6.0 Complaints

A Complaint is any written, electronic, or oral communication that alleges deficiencies related to the physical characteristics, identity, quality, purity, potency, durability, reliability, safety, effectiveness, or performance of a product/device after it is released for distribution.

Complaints associated with any component of this investigational product must be reported to the Sponsor (Section 6.1.6). For adverse events, please refer to Sections 6.1 through 6.1.8.

6.1 Medical Complaints

The investigator will monitor each subject for clinical and laboratory evidence of adverse events on a routine basis throughout the study. The investigator will assess and record any adverse event in detail including the date of onset, event diagnosis (if known) or sign/symptom, severity, time course (end date, ongoing, intermittent), relationship of the adverse event to study drug, and any action(s) taken. For serious adverse events considered as having "no reasonable possibility" of being associated with study drug, the investigator will provide an Other cause of the event. For adverse events to be considered intermittent, the events must be of similar nature and severity. Adverse events, whether in response to a query, observed by site personnel, or reported spontaneously by the subject will be recorded.

All adverse events will be followed to a satisfactory conclusion.

6.1.1 Definitions

6.1.1.1 Adverse Event

An adverse event is defined as any untoward medical occurrence in a patient or clinical investigation subject administered a pharmaceutical product and which does not necessarily have a causal relationship with this treatment. An adverse event can therefore be any unfavorable and unintended sign (including an abnormal laboratory finding), symptom, or disease temporally associated with the use of a medicinal (investigational) product, whether or not the event is considered causally related to the use of the product.

Such an event can result from use of the drug as stipulated in the protocol or labeling, as well as from accidental or intentional overdose, drug abuse, or drug withdrawal. Any worsening of a pre-existing condition or illness is considered an adverse event.

Worsening in severity of a reported adverse event should be reported as a new adverse event. Laboratory abnormalities and changes in vital signs are considered to be adverse events only if they result in discontinuation from the study, necessitate therapeutic medical intervention, meet protocol specific criteria (see Section 6.1.8 regarding toxicity management), and/or if the investigator considers them to be adverse events.

An elective surgery/procedure scheduled to occur during a study will not be considered an adverse event if the surgery/procedure is being performed for a pre-existing condition and the surgery/procedure has been pre-planned prior to study entry. However, if the pre-existing condition deteriorates unexpectedly during the study (e.g., surgery performed earlier than planned), then the deterioration of the condition for which the elective surgery/procedure is being done will be considered an adverse event.

A treatment-emergent adverse event is defined as any adverse event reported by a subject with onset or worsening from the time that the first dose of study drug is administered until 30 days have elapsed following discontinuation of study drug administration.

6.1.1.2 Serious Adverse Events

If an adverse event meets any of the following criteria, it is to be reported to AbbVie as a serious adverse event **within 24 hours** of the site being made aware of the serious adverse event:

Death of Subject	An event that results in the death of a subject.
Life-Threatening	An event that, in the opinion of the investigator, would have resulted in immediate fatality if medical intervention had not been taken. This does not include an event that would have been fatal if it had occurred in a more severe form.
Hospitalization or Prolongation of Hospitalization	An event that results in an admission to the hospital for any length of time or prolongs the subject's hospital stay. This does not include an emergency room visit or admission to an outpatient facility.
Congenital Anomaly	An anomaly detected at or after birth, or any anomaly that results in fetal loss.
Persistent or Significant Disability/Incapacity	An event that results in a condition that substantially interferes with the activities of daily living of a study subject. Disability is not intended to include experiences of relatively minor medical significance such as headache, nausea, vomiting, diarrhea, influenza, and accidental trauma (e.g., sprained ankle).
Important Medical Event Requiring Medical or Surgical Intervention to Prevent Serious Outcome	An important medical event that may not be immediately life-threatening or result in death or hospitalization, but based on medical judgment may jeopardize the subject and may require medical or surgical intervention to prevent any of the outcomes listed above (i.e., death of subject, life-threatening, hospitalization, prolongation of hospitalization, congenital anomaly, or persistent or significant disability/incapacity). Additionally, any elective or spontaneous abortion or stillbirth is considered an important medical event. Examples of such events include allergic bronchospasm requiring intensive treatment in an emergency room or at home, blood dyscrasias or convulsions that do not result in inpatient hospitalization, or the development of drug dependency or drug abuse

For serious adverse events with the outcome of death, the date and cause of death will be recorded on the appropriate case report form. Deaths related to disease progression will not be recorded as serious adverse events (see Section 6.1.3.1).

Hospitalization of a subject to allow observation and management (e.g., for IV hydration) for the purpose of TLS prophylaxis will not be captured as a serious adverse event (SAE), unless there is an additional reason for hospitalization or an additional criterion for seriousness other than hospitalization (e.g., abnormal post-dose TLS laboratories that necessitate therapeutic medical intervention, etc.). Additional criteria for defining TLS are in [Appendix H](#).

6.1.1.3 Adverse Events Commonly Associated with Acute Myelogenous Leukemia Study Population and/or Progression of Acute Myelogenous Leukemia

Certain adverse events are anticipated to occur in the study population (AML) at some frequency independent of drug exposure. Such events include known consequences of the underlying disease or condition under investigation (e.g., symptoms, disease progression) and events unlikely to be related to the underlying disease or condition under investigation but common in the study population independent of drug therapy (e.g., cardiovascular events in an elderly population).

These events are listed in [Appendix F](#) (Adverse Events Commonly Associated with AML Study Population or Progression of AML).

These adverse events may occur alone or in various combinations and are considered expected for reporting purposes for this protocol.

Cytopenias (anemia, neutropenia, or thrombocytopenia) are part of the natural history of AML. Persistent cytopenias at the same CTCAE grade as at baseline are not to be reported as adverse events, unless they fulfill a seriousness criteria, result in permanent discontinuation of a study drug, or the investigator had an identifiable cause other than the

underlying disease. However, all laboratory data should be entered regardless of whether an adverse event is reported.

Although exempted from expedited reporting to Health Authorities and IRBs as individual cases, if an event commonly associated with AML or progression of AML meets seriousness criteria (as defined in Section 6.1.1.2) it must be reported to AbbVie within 24 hours of the site being made aware of the serious adverse event. For deaths related to disease progression, the date and cause of death will be recorded on the appropriate case report form, but the death will not be expedited as an individual case safety report (ICSR) to regulatory authorities.

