6.1.8.3 Management of Myelosuppression (Cytopenias)

Venetoclax

Myelosuppression and the related adverse events (thrombocytopenia, anemia, neutropenia, and febrile neutropenia) are common in both treated and untreated subjects with AML. Subjects with baseline neutropenia or have significant bone marrow involvement may be particularly at high risk. If a participant achieves a CR or CRi or is found to have a morphologically leukemia free bone marrow, and has Grade 4 neutropenia or thrombocytopenia, venetoclax should be held from Day 28 until ANC $\geq 500 - 1000/\mu\text{L}$ and platelets $\geq 25 - 100 \times 10^5/\mu\text{L}$. At the investigator's discretion, subjects may resume a subsequent cycle of therapy after a 2-week interruption if the investigator believes the risk of AML progression outweighs the risk of further treatment before cytopenia recovery. Typically, if morphologic AML remains in the bone marrow, concurrent cytopenias are thought to be attributable to the disease processes of AML. In subsequent cycles, if a subject in CR presents with new onset Grade 4 neutropenia or thrombocytopenia for more than 1 week, unless it is due to the underlying disease, venetoclax dosing may be interrupted until ANC recovery to $\geq 500 - 1000/\mu\text{L}$ or platelets $\geq 25 - 100 \times 10^5/\mu\text{L}$ per investigator discretion in consultation with the AbbVie medical monitor. Venetoclax may be re-initiated at a lower dose per discussion with the AbbVie medical monitor.

Administration of venetoclax in subjects with lymphoproliferative disorders has been associated with clinically significant lymphopenia (B and T lymphocyte subtypes). If clinically indicated in AML subjects treated in this study, anti-infective prophylaxis should be implemented at the investigator's discretion, including appropriate prophylaxis for viral, fungal, bacterial or Pneumocystis infections. Potential for drug-drug interactions should be considered. Please refer to [Table 1](#) and [Appendix C](#) for a description of excluded and cautionary medications.

If a subject is continuing to respond based on the bone marrow assessment beyond Cycle 2 of treatment but has persistent neutropenia or thrombocytopenia venetoclax dose may be reduced as follows:

Table 12. Dose Reduction Guidelines for Management of Persistent Neutropenia or Thrombocytopenia

Venetoclax Dose/Duration	Reduced Venetoclax Dose/Duration

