7.6.1 Analysis of Treatment Emergent Adverse Events

Adverse event data will be summarized using system organ classes (SOCs) and preferred terms (PTs) from the Medical Dictionary for Regulatory Activities (MedDRA) Version 21.0 or later for Studies M14-358 and M14-387. Adverse events were coded and summarized in MedDRA Version 18.1 for the Study M14-212 CSR.

For each AE summary, the number and percentage of subjects experiencing at least one AE will be presented (overall) for each dosing group. Subjects reporting more than one AE within a SOC will be counted only once for that SOC. Subjects reporting more than one AE for a PT will be counted only once for that PT.

For summaries of AEs by the National Cancer Institute Common Toxicity Criteria (NCI CTC) grade, at each level of summation (overall, SOC, and PT) each subject is counted only once at the maximum grade level. The number and percentage of subjects experiencing at least one event for each of the following events will be summarized (but not limited to):

- Any TEAE.
- Any TEAE with reasonable possibility related to venetoclax by the investigator.
- Any TEAE with NCI toxicity (CTCAE V4.0) Grade 3, 4, or 5 adverse events.
- Any TEAE with NCI toxicity (CTCAE V4.0) Grade 3 or 4 adverse event.
- Any treatment-emergent serious AE (SAE).
- Any TEAE leading to discontinuation of venetoclax.

- Any TEAE leading to venetoclax dose interruption.
- Any TEAE leading to venetoclax dose reduction.
- Any TEAE leading to hospitalizations.
- Any TEAE of special interest (AESI) (Section 7.6.2).
- Any TEAE leading to death.
- Any TEAE with reasonable possibility related to HMA (Study M14-358) or LDAC (Study M14-387) by the investigator.
- Any TEAE leading to discontinuation of HMA (Study M14-358) or LDAC (Study M14-387).
- Any TEAE leading to HMA (Study M14-358) or LDAC (Study M14-387) dose interruption.
- Any TEAE leading to HMA (Study M14-358) or LDAC (Study M14-387) dose reduction.

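### Safety tables of TEAEs leading to dose interruption or reduction can undercount dose changes made for cytopenias that persist at their baseline grade

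*Protocol*

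**What the plan says.** **Recording rule.** Protocol Section 6.1.1.3 says: "Persistent cytopenias at the same CTCAE grade as at baseline are not to be reported as adverse events, unless they fulfill a seriousness criteria". The sentence goes on to except events that "result in permanent discontinuation of a study drug, or the investigator had an identifiable cause other than the" leukemia itself. The same paragraph requires all laboratory data to be entered whether or not an adverse event is reported.

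**General rule.** Section 6.1.1.1 treats laboratory abnormalities as adverse events only in listed situations. Two of these are that they "meet protocol specific criteria (see Section 6.1.8 regarding toxicity management), and/or if the investigator considers them to be adverse events".

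**Dose rules.** Section 6.1.8.3 covers subjects with CRi or CR, and also one who "is found to have a morphologically leukemia free bone marrow, and has Grade 4 neutropenia or thrombocytopenia, venetoclax should be held from Day 28". For a subject who is still responding by marrow beyond Cycle 2 but "has persistent neutropenia or thrombocytopenia venetoclax dose may be reduced as follows", Table 12 gives three steps. It states no grade.

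**Analysis.** Safety SAP 7.6.1 lists "Any TEAE leading to venetoclax dose interruption", with matching rows for venetoclax reduction and for interruption and reduction of LDAC. Safety SAP 7.6 defines a TEAE by onset or worsening after the first dose.

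**The concern.** A hold or a reduction can be directed by the protocol without an adverse event having to be recorded, because only permanent discontinuation appears among the exceptions in Section 6.1.1.3. Section 6.1.1.1 points the other way for a cytopenia that triggers a Section 6.1.8.3 action. Two sites could each follow the protocol and record the same case differently.

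The affected rows are important tolerability outputs for a myelosuppressive combination, and characterizing toxicity is a primary objective of the initial Phase 2 portion (Protocol Section 4.0). There is also an awkward asymmetry. CRi is defined by residual neutropenia or thrombocytopenia (Section 5.3.3) and counts toward ORR (Section 8.1.3). The same subject can be an efficacy success while the hold or reduction for the persisting cytopenia is absent from the tolerability rows.

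**Working it through.** The plan gives no figure to reproduce, so the check sets the rules side by side and asks which dose changes can escape.

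1. **Subject in CR.** CR requires ANC of at least 10^3/µL and platelets of at least 10^5/µL (Section 5.3.3). A later Grade 4 count is a fall after recovery, not a persistent cytopenia. The exemption does not apply.
2. **Later-cycle interruption.** Section 6.1.8.3 makes this depend on new-onset Grade 4. The exemption does not apply.
3. **Day 28 hold, baseline below Grade 4.** Reaching Grade 4 is a worsening and so a TEAE. The exemption does not apply.
4. **Day 28 hold, Grade 4 at baseline and unchanged, with CRi or leukemia-free marrow.** The exemption can apply unless the investigator identifies a cause other than the disease.
5. **Table 12 reduction.** The trigger is persistence and no grade is set, so an unchanged baseline cytopenia of any grade can qualify. This is the most exposed part.
6. **If the site records cases 4 or 5 under Section 6.1.1.1.** The event may still fail the onset-or-worsening test in Safety SAP 7.6 and drop out of the 7.6.1 rows.

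**Do the other outputs fill the gap?** Safety SAP 7.3 defines two dose-intensity ratios for venetoclax. Dose intensity due to reduction leaves dose-free days out of the planned total; dose intensity due to reduction and interruption includes them. For a full 28-day cycle, assuming the planned daily dose stays at 600 mg (7.3 does not say):

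| Schedule | Actual dose | Ratio for reduction | Ratio for reduction and interruption |
|---|---|---|---|
| Full | 28 × 600 = 16,800 mg | 16,800/16,800 = 100% | 16,800/16,800 = 100% |
| Step 1 | 21 × 600 = 12,600 mg | 12,600/(21 × 600) = 100% | 12,600/16,800 = 75% |
| Step 2 | 14 × 600 = 8,400 mg | 8,400/(14 × 600) = 100% | 8,400/16,800 = 50% |
| Step 3 | 14 × 400 = 5,600 mg | 5,600/(14 × 600) = 66.7% | 5,600/16,800 = 33.3% |

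The first ratio does not show steps 1 and 2 at all. The second shows them, but it gives no count of subjects with a dose change and no reason for it. For LDAC, 7.3 summarizes only the number of cycles.

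The grade cross-tabulation in Safety SAP 7.7.1 keeps a subject who stays at Grade 4, but the count of shifts from Grade 0–2 to Grade 3–4 cannot include that subject. Neither links a laboratory value to a dose change.

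**Size.** It would need the distribution of baseline grades, the frequency of holds and reductions, and how investigators attribute the cytopenias. The documents give none of these.

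**The case against.** The strongest reply is that the third exception already covers most of what is left. The cases in question have a marrow that is clear or still responding, and Section 6.1.8.3 says: "Typically, if morphologic AML remains in the bone marrow, concurrent cytopenias are thought to be attributable to the disease processes of AML". Once the marrow has cleared, a cause other than the disease is the natural reading, and the event becomes reportable. This has real weight and probably brings many cleared-marrow holds back. It does not close the gap. The call is left to the investigator, no text says that clearance makes the drug the identifiable cause, and a recorded event of unchanged grade may still not be a TEAE.

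A second reply is that Sections 6.1.1.1 and 6.1.1.3 do not truly conflict, because a specific carve-out ordinarily qualifies a general rule. That is a fair reading, but the protocol does not state it. On that reading the gap stands; on the other reading, recording improves but the TEAE test remains.

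A third reply is that dose intensity and laboratory shifts do not depend on AE recording. That is correct, and a reader who infers that dose changes vanish from the safety report altogether would be wrong. What is missing is a subject count and a link to the cytopenia.

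A reader might also infer that cytopenia is the protocol's main reason for changing dose. The protocol does not say so: TLS (6.1.8.2), nonhematologic toxicity (6.1.8.5) and CYP3A inhibitor use (Table 2) also lead to changes. Table 12 is only the one tabulated reduction schedule for toxicity.

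**Conclusion.** The point holds in a limited form. The rows for TEAEs leading to interruption or reduction can omit dose changes made for a cytopenia that has stayed at its baseline grade. These are mainly Table 12 reductions, together with Day 28 holds in subjects at Grade 4 at baseline with CRi or leukemia-free marrow. As a count of dose changes the error runs one way, because the exemption can only remove events.

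It does not follow that drug toxicity is understated by the same amount, since some of the omitted cytopenias will be due to AML. Nor do the documents show that such events always go unrecorded; they show only that they need not be recorded.

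A reader might try to size the gap by multiplying an assumed share of subjects at Grade 4 at baseline by an assumed share held or reduced. The result would rest wholly on the assumptions, and it would ignore marrow clearance and the exceptions in Section 6.1.1.3. No number of affected subjects is supported. The summaries are descriptive and no formal test is planned (efficacy SAP 9.0), so the consequence is for the tolerability description. The remedy is cheap enough to be worth making.

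**What to change.** **Protocol.** Reconcile Sections 6.1.1.1 and 6.1.1.3, so that one statement says whether a baseline-grade cytopenia that triggers a Section 6.1.8.3 action is recorded as an adverse event. This concerns recording only; no dosing rule changes. It will not repair the tables by itself. The onset-or-worsening requirement remains, the safety SAP reports enrollment as complete, and a late change of rule would mix two recording conventions in one dataset.

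**Safety SAP 7.3 and 7.6.1.** Add the number and percentage of subjects with any venetoclax or LDC interruption, delay, or reduction in dose or dosing days. Take these from the dosing record regardless of AE linkage. Break them down by recorded reason where available and by ANC and platelet grade at the time, and print them beside the TEAE-based rows.

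**Cost.** One extra derived table. The venetoclax dose data are already needed for the 7.3 ratios, and Section 6.1.1.3 requires all laboratory data to be entered. LDC detail depends on what the dosing record holds. Reported dose-modification rates may be higher and will include some disease-caused cytopenias, which a footnote should say.

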6.1.2 Adverse Event Severity

The investigator will rate the severity of each adverse event according to the National Cancer Institute Common Terminology Criteria for Adverse Events (NCI CTCAE Version 4.0).⁴⁰ If a reported adverse event increases in severity, the initial adverse event should be given final outcome date and a new adverse event must be reported to reflect the change in severity. The dates on the adverse events cannot overlap. For all reported serious adverse events that increase in severity, the supplemental eCRFs also need to be updated to reflect any changes due to the increase in severity.

For adverse events not captured by the Common Terminology Criteria, the following should be used:

- Grade 1** The adverse event is transient and easily tolerated by the subject (mild).
- Grade 2** The adverse event causes the subject discomfort and interrupts the subject's usual activities (moderate).
- Grade 3** The adverse event causes considerable interference with the subject's usual activities and may be incapacitating (moderate to severe).
- Grade 4** The adverse event is life threatening requiring urgent intervention (severe).
- Grade 5** The adverse event resulted in death of the subject (severe).

6.1.3 Adverse Events Expected Due to Study Related Endpoints

6.1.3.1 Deaths

For this protocol, overall survival is an efficacy endpoint.

Deaths that occur during the protocol-specified adverse event reporting period (see Section 6.1.5) that are attributed by the investigator solely to progression of AML should be recorded only on the Study Completion and Death eCRF. All other on-study deaths, regardless of relationship to study drug, must be recorded on the Adverse Event eCRF and immediately reported to the Sponsor (see Section 6.1.6).

Death should be considered an outcome and not a distinct event. The event or condition that caused or contributed to the fatal outcome should be recorded as the single medical concept on the Adverse Event eCRF. Generally, only one such event should be reported. The term "sudden death" should only be used for the occurrence of an abrupt and unexpected death due to presumed cardiac causes in a patient with or without pre-existing heart disease, within 1 hour of the onset of acute symptoms or, in the case of an unwitnessed death, within 24 hours after the patient was last seen alive and stable. If the cause of death is unknown and cannot be ascertained at the time of reporting, "unexplained death" should be recorded on the Adverse Event eCRF. If the cause of death later becomes available (e.g., after autopsy), "unexplained death" should be replaced by the established cause of death.

